# 54 Describe any necessary procedures for ensuring the safety of a participant who has withdrawn early.

To input text, click in the light grey area below.

There are no procedures in place to ensure the safety of a participant that is withdrawn for abusive or inappropriate behavior toward callers. This is a minimal risk study and being withdrawn poses no risk to the participant.

# 55 Describe any pre-specified criteria for stopping or changing the study protocol due to safety concerns.

To input text, click in the light grey area below.

# REQUIRED DISCLOSURES

## Required Consent Disclosures

Identify each element below that may require additional information to be disclosed in the consent form.

*Click on the check box (or double click and type an "X" if using Google Docs).* 

# It is reasonable that researchers could discover or suspect child or elder abuse. It is reasonable that researchers could learn of an incident that could require reporting under Title IX. It is reasonable that researchers could discover incidental findings or other information of medical interest about a participant's previously unknown condition.

# 59 Articulate methods for addressing and reporting incidental findings, if applicable.

To input text, click in the light grey area below.

If during the study, we learn about child or elder abuse or neglect, or that someone is a clear, serious, and direct harm to self or others, we may report the information to the appropriate authorities, including the police, the Texas Department of Family and Protective Services, Lone Star Circle of Care and/or an emergency medical facility.

In the event a participant includes a response of 1-3 on the PHQ-9 question #9, the following protocol will be activated:

- 1. REDCap real-time notification via email to assigned research staff person while participant completes remaining surveys
- 2. Research team alerts Dr. [name], Director of Psychiatry and BH at LSCC, immediately and normal LSCC procedures will occur to escalate issue to offer resources (direct phone call by BH provider)

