**Measure Collection:** Biomedical measures will be directly collected in person at their clinic site, Dell Medical School at The University of Texas at Austin, or a community site that is convenient (A1C and Blood pressure). Patient-reported measures will be collected through self-report on a tablet (or paper copy if participant chooses) at the same time biomedical measures are collected. Electronic Health Record measures will be collected via a data agreement with Lone Star Circle of Care (LSCC).

Measure	Freq	ΤοοΙ	
Program Effects			
Hemoglobin A1C	Baseline/3 mths/6 mths/9 mths/12mths	Finger stick on portable device	

Blood Pressure	Baseline/3 mths/6 mths/9 mths/12mths	Automatic blood pressure cuff
Depression	Baseline/3 mths/6 mths/9mths/12 mths	PHQ-9
Anxiety	Baseline/3 mths/6 mths/9 mths/12 mths	GAD-7
General Health	Baseline/3 mths/6 mths/9 mths/12 mths	SF-12
Healthcare Utilization (PCP & BH clinic, Hosp, ED visits)	Baseline/3 mths/6 mths/9 mths/12 mths	Customized (4 new questions added)
Healthcare Utilization (PCP visits, BH visits)	Data pulls for data collected during program	LSCC ElecHealthRecord
Medication Related to DM and HTN	Baseline/3 mths/6 mths/9 mths/12mths	Customized
Medication Adherence Survey	Baseline/3 mths/6 mths/9 mths12 mths	Med Adherence Report Scale (MARS 5)
Diabetes Self-Management	Baseline/3 mths/6 mths/9 mths/12 mths	Perceived Diabetes Self- Management Scale (PDSMS)
Diabetes Self Care	Baseline/3 mths/6 mths/9 mths/12 mths	Summary of Diabetes Self-Care Activities (SDSCA)
Diabetes Self Efficacy	Baseline/3 mths/6 mths/9 mths/12 mths	Stanford Self-Efficacy for Diabetes Scale
Diabetes Distress	Baseline/3 mths/6 mths/9 mths/12 mths	Diabetes Distress Screening Scale
Loneliness	Baseline/3 mths/6 mths/9 mths/12 mths	UCLA 3-item Loneliness Scale
Onset Date of Diabetes	Baseline	Customized
Social Needs Survey	Baseline/6 mths/12 mths	Adapted from PRAPARE
Social Support	Baseline	Lubben Social Network scale
Participant Demographics	Baseline	Customized
Household demographics	Baseline	Customized
Interest in Calling Others	6 mths	Customized
Program Satisfaction	6 mths (intervention arm only)	Customized
Program Improvement	12 mths (intervention arm only)	Customized
Program Implementation		
Call Occurrence	Continuous (daily; did it happen)	Twilio report
Call Connection	Continuous (daily; did the call connect to a person)	Twilio report
Call Duration	Continuous (daily); for every call placed, duration	Twilio report

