#### b. Consent

- i. Interested participants will be called by study staff to screen and share consent information. Consent will then be signed electronically, through DocuSign, or for those that do not complete this, the first time they come to a clinic site, Dell Medical School at The University of Texas at Austin, community-based site, or on rare occasion in people's homes, for baseline measurement, they will sign in person. No research activities will take place before informed consent is completed.
- 2. Measure collection
  - a. General: Research associates/study staff will collect biomedical measures. Participants will fill out their own surveys on iPads/tablets at the measure collection site. Paper copies will be available for participants to complete upon request. Research associates will be blinded to the status of the participants.
  - b. First measure collection
    - i. After phone screening and consent, the participant will be invited to come the clinic site, Dell Medical School at The University of Texas at Austin, other community-based site, or on rare occasion in people's homes on weekends and/or in the evenings and given choices on when to schedule measurement collection. When they come to the site, they will get a chance to sign consent forms if they haven't done so electronically; then study staff will collect A1C and blood pressure measurements. After this, participants will use a tablet or paper copy to answer survey information. The survey

information will be saved directly into a RedCap database. The paper copy of the responses, if used, will be stored in a locked cabinet.

- c. Subsequent measure collections (3, 6, 9 and 12 months)
  - i. Similar to above, without informed consent process.
  - ii. The program improvement survey, administered at the 12-month (last) measurement visit will only be collected once, during the 12month visit. It will be collected from intervention participants only via the electronic tablet where all other measures are answered.
- 3. Randomization
  - a. To ensure that the effect of the empathy calls program can be assessed without confounding it with depressive mood, we will rely on stratified randomization so that approximately 50% (N=75) of the individuals in both the control and experimental group have a PHQ9 > 5 at baseline and 50% of the individuals have PHQ9 < 5 at baseline. Randomization will occur after participant consent and collection of baseline measures.
- 4. Program Intervention

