#### To input text, click in the light grey area below.

- a. Interest List
  - i. A participant qualifying list will be created by Lone Star Circle of Care (LSCC) to include patients who meet inclusion and do not meet exclusion criteria. Individuals with authorization will collect the initial PHI to create a list of patients that would like to be contacted by the research team. They will provide this list of names, e-mails, and phone numbers to the research team so we can call and provide detailed information about the research and determine if patients would like to participate. Messages will be sent out on the LSCC Care Message text platform or email to identify interested participants from this database.
  - ii. Lone Star Circle of Care (LSCC) staff will use flyers created by the team (and submitted with this IRB submission) to identify interested patients.
  - iii. LSCC staff creating the interest list will be considered research team members and will be added to the IRB once they have been selected and trained (CITI).
- b. Consent
  - i. Interested patients will be called by study staff to screen and share consent information. Consent will then be signed electronically, through DocuSign, or for those that do not complete this, the first time they come to their regular LSCC clinic site, Dell Medical School at The University of Texas at Austin, or community-based site, for baseline measurement, they will sign in person.
- c. Measure collection A1C measure
  - i. Research associates/study staff will collect HbA1C at in person visit after consent is signed. Individuals with HbA1C less than 7.5 will be considered a screen fail.
- d. Measure collection PHQ-9
  - i. After consent is signed and HbA1C is measured during the first inperson visit, research associates/study staff will give a tablet or paper copy to the participant for them to complete the questionnaires. One of the first few questionnaires is the PHQ-9, which will have all questions marked as required, so that the participant cannot move ahead in the surveys unless each question is answered. This approach is needed to ensure adequate and fair stratified randomization. Participants that flag to the research associates/study staff that they do not want to complete the PHQ-9 questionnaire will be informed that they will not be able to join the study.

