#### To input text, click in the light grey area below.

Participant privacy will be maintained by conducting research visits in a private room or if in a large space, by providing adequate distance to ensure privacy. Surveys will be completed by participants using tablets further ensuring privacy. If participant chooses to complete surveys with a hard copy, it will be stored in a locked cabinet before and after measurement collection. All intervention procedures (phone calls) will be conducted using a phone number provided by the participant.

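### The only listed way to detect a PHQ-9 item-9 answer of 1 to 3 is a real-time REDCap email, which cannot fire during the visit for the paper forms the plan allows

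*Combined protocol and SAP*

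**What the plan says.** Section 59 sets the trigger without regard to survey format: "In the event a participant includes a response of 1-3 on the PHQ-9 question #9, the following protocol will be activated". Step 1 is "REDCap real-time notification via email to assigned research staff person while participant completes remaining surveys". Step 2 has the research team alert the LSCC behavioral health lead at once, after which a behavioral health provider phones the participant.

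The table of measures in Section 4 schedules the PHQ-9 at baseline and at months 3, 6, 9 and 12. Paper is a permitted format. Section 11, item 2a states: "Paper copies will be available for participants to complete upon request". Section 19, item d, which covers the PHQ-9 at the first visit, says that staff "will give a tablet or paper copy to the participant for them to complete the questionnaires".

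On what happens to a paper form, Section 11, item 2b says: "The paper copy of the responses, if used, will be stored in a locked cabinet". Section 60 says: "If participant chooses to complete surveys with a hard copy, it will be stored in a locked cabinet before and after measurement collection". Section 62a adds that paper responses go into REDCap and that the form is kept locked until it is destroyed. It gives no time for the entry.

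**The concern.** The plan has already decided that an item-9 answer of 1 to 3 calls for notice during the visit and immediate escalation. The mechanism chosen to deliver that notice depends on the answer being in REDCap while the participant is still filling in surveys. A tablet answer meets that condition and a paper answer does not.

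Two participants who give the same answer could therefore be handled differently because of format alone. The tablet user is flagged while still on site. The paper user may leave with nobody having seen the answer, and the LSCC phone call may be prompted only when the form is entered. Section 11 allows visits at community sites, in evenings, on weekends and occasionally at home, so clinic staff may not be nearby to notice anything else. What is at stake is participant safety. The primary estimate, the power and the analysis are not touched.

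**Working it through.** The plan gives no figure to reproduce, so the check is to follow one item-9 answer of 1 to 3 through the text in each format.

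1. **Trigger.** Section 59 applies to any answer of 1 to 3. Format does not matter, so a paper answer is covered by the rule.
2. **Detection, tablet.** Section 11, item 2b has survey answers saved directly to REDCap. The email can be sent while later questionnaires are being completed, and step 1 works.
3. **Detection, paper.** The answer is not in REDCap during completion, so no email can be sent then. An alert could still fire at data entry. Section 59 lists no other detection step, and the safety-monitoring detail fields (Sections 45 to 52) hold no entries that would supply one.
4. **Time to entry.** Sections 11, 60 and 62a cover storage and state that entry will happen. None says when.
5. **Reading the form on site.** No section has staff look at item 9 before the participant leaves. Section 4 (Blinding) relies on self-completion by tablet or paper to keep research associates blinded, which gives them a reason not to look through a packet.
6. **Escalation.** Step 2 is immediate, but only from the moment the research team knows. With steps 3 to 5 unspecified, the interval from answer to escalation is unspecified as well.

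**Baseline against follow-up.** At baseline, Section 13 makes a complete PHQ-9 a condition of entry, and Section 11, item 3 stratifies on the score and states: "Randomization will occur after participant consent and collection of baseline measures". A paper form must therefore be scored before randomization. That prompts someone to read it, but no hour or day is set, and the participant may already have left. At months 3, 6, 9 and 12 no later step needs the score, so nothing prompts scoring.

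**Blank items.** Section 19, item d marks every PHQ-9 question as required so that the participant cannot move on. It is described for the first visit, and it can work only on a tablet. Paper has no equivalent.

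**Size.** With 300 participants (Section 14) and five visits, 300 × 5 = 1,500 PHQ-9 forms are scheduled. This is the total in all formats if no visit is missed, and it is not an estimate of affected forms. That would need the share completed on paper and the share of those with item 9 at 1 to 3, and the documents give neither.

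**The case against.** The strongest reply is that the plan is silent on timing and does not mandate delay. The trigger is compulsory and format-neutral, step 2 is immediate, the privacy wording does not bar reading the form during the visit, and Section 62a mentions REDCap entry ahead of storage, which is consistent with entry before filing. This stands as far as it goes. A reader might infer that escalation can be delayed without limit, or that a blank item 9 on paper will go unnoticed. The documents support neither; they support only that timing and checking are not specified.

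A reader might also infer that baseline is safe and that exposure lies in the four follow-up visits, 1,200 of 1,500 forms (80%). That split does not measure exposure. Baseline has no same-visit deadline either, and the paper share at each visit is unknown.

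A further reply is that Section 59 has a general clause on serious harm to self or others. It is not limited to surveys: a participant might speak up at a visit, and intervention participants also talk with callers. It would be wrong to say that this route depends on someone reading the form. But it covers what the team may do once it learns of a danger, and it does not bring a silent paper answer to light. Control participants receive no calls.

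Finally, paper users may be few, and Section 13e excludes serious mental illness. Both points limit the likely frequency. Neither makes step 1 work on paper.

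**Conclusion.** The concern holds in this form: followed as written, Section 59 cannot give a paper user the same-visit alert that it gives a tablet user, and no other text sets a time for reading or entering the form. This applies at all five visits. Baseline has a prompt to score before randomization but no same-visit deadline; the later four visits have no prompt.

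The number of participants affected cannot be stated, because tablet is the default, paper is on request, and no paper share or item-9 rate is given. The conclusion rests on one assumption: that no working instruction outside these documents already has staff check paper forms. The normal LSCC procedures named in step 2 do not fill the gap, since they begin after the alert.

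This should be corrected because it concerns safety and costs little. It is not a threat to the trial's primary result.

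**What to change.** Add a paper branch to Section 59, for example:

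> If the PHQ-9 is completed on paper, the assigned research staff person checks item 9 before the participant leaves. If it is blank, they ask the participant to complete it or confirm that they decline. If the answer is 1 to 3, they start step 2 at once. The PHQ-9 is entered in REDCap the same day.

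Three details protect blinding:

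- Print the PHQ-9 on its own sheet. The person checking then does not see arm-revealing 6-month items, such as the intervention arm's satisfaction survey or the controls' tool and gift choices.
- Do the check after A1C and blood pressure have been taken. Section 11, item 2b already has that order for the first visit, and item 2c describes later visits as similar.
- Where possible, use someone already on the team who does not measure that participant's A1C.

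The cost is a few lines of text, a separate sheet, and a short check at each paper visit (about a minute, assumed), with no extra staff. There are two small downsides. Staff will see paper users' PHQ-9 answers. The brief conversation also carries a slight unblinding risk for later A1C measurements: an intervention participant might mention their caller at month 3, before the 6-month primary measurement. So it should not be claimed that the primary outcome is wholly untouched by the change; the three details above keep the risk low.

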# PRIVACY AND CONFIDENTIALITY

#### 60 Privacy

Describe how you will protect the identity and privacy of study participants during each phase of research. Privacy focuses on the individual participants rather than data. In this section, researchers should focus on issues such as where research activities take place and how participant involvement is protected from nonparticipants.

Describe methods to ensure participants' privacy during identification, recruitment, screening, the consent process, the conduct of the study, and dissemination of data.

#### To input text, click in the light grey area below.

Participant privacy will be maintained by conducting research visits in a private room or if in a large space, by providing adequate distance to ensure privacy. Surveys will be completed by participants using tablets further ensuring privacy. If participant chooses to complete surveys with a hard copy, it will be stored in a locked cabinet before and after measurement collection. All intervention procedures (phone calls) will be conducted using a phone number provided by the participant.

#### **Confidentiality and Data Security Plan**

Click on the check box (or double click and type an "X" if using Google Docs) that best describes the confidentiality and data security plan and provide additional details regarding how you will protect the confidentiality of data or address confidentiality concerns.

#### **61** Identifiers will be coded to protect confidentiality.

61a If true, state how data is coded and where identifiers are stored. To input text, click in the light grey area below.

#### 62 🛛 Identifiable data will be destroyed.

#### 62a If true, describe destruction plan and timeline

#### To input text, click in the light grey area below.

[figure not shown]
Identifiers will be destroyed at the end of the study after all data has been analyzed. All data will be stored in the Dell Med REDCap database. This secure, HIPAA compliant database can only be accessed with password and dual authentication. Hard copies of the measurements will be available to participants upon request. If participant chooses to complete measurements with a paper copy, responses will be entered in the REDCap database, and the paper copy will be stored in a locked cabinet until it is destroyed with the other data (after it has been analyzed).

- **63 Identifiable data will not be destroyed.** 
  - 63a If true, provide rationale for retaining identifiable data indefinitely. *To input text, click in the light grey area below.*

# 64 Data Access

*Click on the check box (or double click and type an "X" if using Google Docs) for each group of individuals that will have access to study data.* 

If you plan on creating a repository, complete the repository form as well.

65 Describe data sharing plan for each group checked above and state whether researchers plan on sharing identifiable, coded, or de-identified data *To input text, click in the light grey area below.* 

No identifiable research data will be shared outside of the research team. Aggregate data will be shared with LSCC and presented in public.

We may share data with other researchers for future research studies that may be similar to this study or may be very different. The data shared with other researchers will not include information that can directly identify the participant

# **Certificate of Confidentiality**

*Click on the check box (or double click and type an "X" if using Google Docs) to identify each element below that may require additional information to be disclosed in the consent form.* 

If a Certificate of Confidentiality is not applicable for this study, skip to 68.

- **66 D** The study requires a Certificate of Confidentiality.
- **67** I NIH has issued a Certificate of Confidentiality for this study.

68

A Certificate of Confidentiality has not been obtained, but there are plans to apply for one.

# COMPENSATION AND COSTS

#### Compensation

*Click on the check box (or double click and type an "X" if using Google Docs).* 

- 69 Subjects receive compensation.
- **70** Subject will not receive compensation. *Skip to question 74 if subjects will not receive compensation.*
- 71 Total Amount of Compensation

To input text, click in the light grey area below.

Participants will be paid \$50.00 for each measurement visit for a maximum of \$250.00 for 5 visits.

#### 72 Type of Compensation

*Click on the check box (or double click and type an "X" if using Google Docs) for each form of compensation that will be provided.* 

Cash	Check	$\boxtimes$	Gift Card
Course Credit	ClinCard	$\boxtimes$	Tango Card
Other			
Describe, To input text, click in the light grey area below.			

#### 73 Proration Schedule

[figure not shown]
To input text, click in the light grey area below.

Participants will be paid \$50.00 for each measurement visit for a maximum of \$250.00 for 5 visits.

# **74** Amount of compensation and its form is reasonable for this population for the activities requested of them.

75 Costs

*Click on the check box (or double click and type an "X" if using Google Docs) each applicable item regarding costs.* 

To input text, click in the light grey area below.

76

There is a small cost to travel to the study visit sites. This will vary from one participant to the next, but will be negligible for most.
